3.2. Secondary study endpoints

- Per-protocol analysis of sensitivities and specificities of Ultra on stool using TB culture reference standard (LJ ans MGIT) in respiratory sample, excluding invalid Ultral results and contaminated culture results from analysis.
- Head-to-head comparisons
 - o Sensitivities and specificities of each sampling method using TB culture reference standard.
 - Sensitivities and specificities of each sampling method using the TB composite reference standard as defined by the Expert Committee (Clinical Case Definition for Classification of Intrathoracic Tuberculosis in Children) [42].
- Head-to-head kappa coefficients.
- Proportions of
 - Ultra "trace" results in stools out of the number of stools tested with Ultra
 - o Ultra semi-quantitative results "very low"; "low"; "medium" and "high" in stool.
 - \circ $\:$ Invalid Ultra results from stool out of the number of stools tested with Ultra
 - Rifampicin resistant results on Ultra (stool and respiratory), LPA and DST
- Stratification of characteristics and laboratory results by age groups (<2 years and > 2 years)
- Proportion of children successfully providing a stool sample
- Relative gain of the 2nd stool sample as compared to the 1st one as measured by the number of additional positive results obtained from the addition of the 2nd sample as compared to the results of the first sample only.
- Feasibility assessment by laboratory technician of their perception of ease of use, safety and suitability to low primary health care setting using a questionnaire and a standard "Ease of use score" [41]

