6.3. Sample flow

Two stool samples over two consecutive days will be collected and transported within 24h to the CTU laboratory for processing and testing. At laboratory, samples will be homogenised and split in four equal aliquots that will be processed with the four processing methods and tested with Ultra (Figure 6).

To avoid experimenter bias, the four aliquots will be processed by the same laboratory technician at the same time.

In case of insufficient stool volume (<5g) another stool sample will be collected.

For cases enrolled from the routine, two GAs or sputum will be collected over two consecutive days. The two respiratory samples will be tested on Ultra and sent for liquid and solid culture.

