11.2. Description of the statistical analysis plan

11.2.1. Analysis of the primary endpoint

Sensitivity of the 4 Ultra on stool using TB culture reference standard (LJ and MGIT) in respiratory sample: point estimate and 95% CIs.

Specificity of the 4 Ultra on stool using TB culture reference standard (LJ and MGIT) in respiratory sample: point estimate and 95% CIs.

We will use as TB culture reference standard:

- Positive: at least one positive MTB culture result in one of the two respiratory samples
- Negative: negative culture results from 2 samples without any positive result

An intention-to-diagnose analysis will be performed at:

- Sample level (denominator: total number of samples collected): 1 stool vs the TB culture reference standard
- Patient level (denominator total number of cases with at least one stool sample collected): at least 1 of the two stools vs the TB culture reference standard.

A patient will be classified as stool positive, when they have at least one positive stool Ultra result (for example the first stool may not have any positive Ultra results, but the second stool could have 1 positive Ultra result, in which case the patient would be considered stool positive).

Invalid Ultra results, contaminated and NTM culture results will be considered negative.

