11.2.2. Analysis of secondary endpoints

- Per-protocol analysis of sensitivities and specificities of Ultra on stool using TB culture reference standard (LJ ans MGIT) in respiratory sample, excluding invalid Ultra results, contaminated and NTM culture results from analysis. Regarding contamination, since two culture methods will be used per respiratory sample (LJ and MGIT), to be excluded both culture results per sample will need to be contaminated.
- Head to head comparison of the sensitivities and specificities between the different stool processing methods using culture reference standard and McNemar test for matched data:
 - Sucrose flotation classic method vs Sucrose Flotation optimised method
 - Sucrose flotation classic method vs SPK method
 - Sucrose flotation classic method vs STEP method
 - Sucrose flotation optimised method vs SPK method
 - Sucrose flotation optimised method vs STEP method
 - SPK method vs STEP method
- Head to head comparison of the sensitivities and specificities between the different stool processing methods using the TB composite reference standard as defined by Clinical Case Definition for Classification of Intrathoracic Tuberculosis in Children, and McNemar test for matched data:
 - Sucrose flotation classic method vs Sucrose Flotation optimised method
 - Sucrose flotation classic method vs SPK method
 - Sucrose flotation classic method vs STEP method
 - Sucrose flotation optimised method vs SPK method
 - Sucrose flotation optimised method vs STEP method
 - SPK method vs STEP method
- Description of results for rifampicin resistance using stool Ultra, respiratory Ultra, LPA and DST
- Agreement of the different stool sample processing methods for Ultra detection head to head using Kappa analysis.
- Comparison of the proportion of rifampicin resistance indeterminate Ultra test results between different stool processing methods using McNemar test for matched data.
- Comparison of the proportion of invalid Ultra test results between different stool processing methods using McNemar test for matched data.
- Comparison of the proportion of Ultra results "trace" between the methods using McNemar test for matched data.
- Proportion of very low, low, medium and high Xpert Ultra results by different methods

- Change in sensitivity and specificity at patient level by using 2 stools vs using just the 1st stool specimen for each processing method.

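### The sample-level primary analysis counts up to two stools per child, so ordinary 95% CIs on it would overstate precision; plain McNemar does not fit the per-stool trace and invalid comparisons

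*Protocol*

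**What the plan says.** Protocol Section 11.2.1 plans the primary analysis at two levels. The first is "Sample level (denominator: total number of samples collected): 1 stool vs the TB culture reference standard". The second is "Patient level (denominator total number of cases with at least one stool sample collected". For both sensitivity and specificity it asks for a "point estimate and 95% CIs"; it names no interval method and does not mention repeated stools from one child.

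Section 6.3 fixes the number of stools per child: "Two stool samples over two consecutive days will be collected".

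Section 3.2 defines a secondary endpoint as "Invalid Ultra results from stool out of the number of stools tested with Ultra", and gives trace results the same per-stool denominator. Section 11.2.2 then plans a "Comparison of the proportion of invalid Ultra test results between different stool processing methods using McNemar test for matched data", with a matching McNemar comparison for trace results. It also plans a "Head to head comparison of the sensitivities and specificities between the different stool processing methods using culture reference standard and McNemar test for matched data", without saying whether the unit is the stool or the child.

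Section 4.3 plans precision in children: 93 with culture-confirmed TB for sensitivity, and 140 culture-negative for specificity.

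**The concern.** Two stools passed about a day apart by the same child are compared with the same culture result, and their Ultra results can be expected to agree more often than two stools from different children. A denominator of all stools therefore holds less information than its size suggests. A standard binomial interval does not know this and comes out too narrow.

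McNemar's test raises a related question. It deals with the pairing of two methods on the same stool, but it assumes that the stool pairs are independent of each other. With two stools per child they need not be.

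At stake are the reported precision of one of the two primary analyses and the p-values for the trace and invalid comparisons between methods. Section 4.1 says the results are meant to contribute to WHO recommendations on stool testing, so the intervals are likely to be read closely.

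**Working it through.** **Inputs from the protocol.** Expected sensitivity 60% with ±10 points, 93 children; expected specificity 90% with ±5 points, 140 children (Section 4.3). Two stools per child (Section 6.3).

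**Assumed.** Every child gives both stools. The protocol gives no within-child correlation ρ, so a range of 0.3 to 0.7 is used, with 1 as the limit.

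**Step 1: the plan's own figures.** n = 1.96² × p(1−p) / d².
- Sensitivity: 1.96² × 0.6 × 0.4 / 0.10² = 92.2, so 93 (stated 93).
- Specificity: 1.96² × 0.9 × 0.1 / 0.05² = 138.3, so 139 (stated 140).

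Both reproduce, to within one child, with children as the independent units.

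**Step 2: unadjusted intervals on all stools.** Half-width = 1.96 × √(p(1−p) / 2n).
- Sensitivity, 186 stools: 1.96 × √(0.24 / 186) = 7.0 points.
- Specificity, 280 stools: 1.96 × √(0.09 / 280) = 3.5 points.

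**Step 3: allowing for clustering.** With two stools per child the design effect is 1 + ρ. The half-width is multiplied by √(1 + ρ), and an unadjusted 95% interval has true coverage 2Φ(1.96 / √(1 + ρ)) − 1.

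| ρ (assumed) | Factor | Sensitivity half-width | Specificity half-width | True coverage of the unadjusted interval |
|---|---|---|---|---|
| 0 | 1.00 | 7.0 | 3.5 | 95% |
| 0.3 | 1.14 | 8.0 | 4.0 | 91% |
| 0.5 | 1.22 | 8.6 | 4.3 | 89% |
| 0.7 | 1.30 | 9.2 | 4.6 | 87% |
| 1 (limit) | 1.41 | 10.0 | 5.0 | 83% |

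At the limit the second stool adds nothing and the half-widths return to those planned for one result per child.

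**Step 4: McNemar with two stools per child.** Simulation of 4,000 trials per scenario: 93 children, two stools each, two methods with equal true positivity of 60%, nominal level 5%. Results came from a latent normal model with total variance 1, made up of a child effect shared by both methods, a child-by-method effect that repeats over both stools, a stool effect and a residual.

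| Child share of variance | Child-by-method share | Stool share | Plain stool-level McNemar, type I error | Test on per-child summed differences |
|---|---|---|---|---|
| 0.70 | 0 | 0.15 | 4.8% | 4.8% |
| 0.70 | 0.05 | 0.10 | 6.8% | 5.4% |
| 0.60 | 0.15 | 0.10 | 7.5% | 5.1% |
| 0.50 | 0.30 | 0.10 | 10.1% | 5.2% |
| 0.40 | 0.50 | 0.05 | 11.6% | 4.1% |

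A child effect common to both methods cancels in the paired difference, so the first row stays at nominal level. Inflation appears only when the difference between methods itself repeats within a child. The simulation uses 60% positivity; it shows the mechanism and is not calibrated to the frequency of trace or invalid results.

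**The case against.** The strongest objection is that the protocol nowhere says stools are treated as independent. It fixes a denominator and asks for 95% intervals, and counting all stools is compatible with clustered intervals. Section 11.1 leaves a separate statistical analysis plan to the study statistician, and the choice of variance estimator is commonly settled there. This stands as a limit on the claim: the overstatement arises if ordinary intervals are used, and the text does not prove that they will be. It does not remove the point, because the plan fixes a primary unit that repeats within the child and, for trace and invalid results, names a test that does not fit the stated unit.

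The sample-level line might also be read as the first stool only, since it speaks of one stool. The denominator of all samples collected contradicts that, and Section 11.2.2 names the first stool explicitly where it means it. At the least, the unit of a primary analysis is unclear.

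A reader might infer that the sensitivity and specificity McNemar tests also use every stool. Section 11.2.2 gives them no unit, and a patient-level result is available from Section 11.2.1, so that inference is not supported. A reader might also infer that stool-level McNemar p-values are always too small; the first simulated row shows otherwise.

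Finally, child-level answers are already planned: the patient-level primary analysis has one result per child, and Section 11.2.2 compares two stools with the first stool alone at patient level. That is correct and limits the harm.

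**Conclusion.** The point holds in a conditional form. If ordinary binomial intervals are put on the sample-level denominator, they overstate precision: ±7.0 points where about 8.0 to 9.2 is right for sensitivity, and ±3.5 where about 4.0 to 4.6 is right for specificity, with coverage of about 91% to 87%. The sizes rest on assumed correlations of 0.3 to 0.7 and on two stools from every child; the direction holds for any positive correlation.

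For trace and invalid results the plain McNemar test can be anti-conservative, at about 7% to 12% in the simulated settings where a method difference repeats within a child, but not where the child effect is common to both methods. The documents do not say which case applies. For the accuracy comparisons, the fault is only that the unit is not stated.

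It would be wrong to conclude that the study is too small or that its planned precision is lost. The sample size counts children, and even at a correlation of 1 the sample-level half-widths are 10.0 and 5.0 points, which is what Section 4.3 planned.

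**What to change.** In Section 11.2.1, either give the sample-level 95% intervals clustered by child (GEE with robust variance, or a bootstrap that resamples children), or define the sample-level analysis on the first stool only.

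In Section 11.2.2, state the unit of every McNemar test. Run the sensitivity and specificity comparisons on one result per child, where the plain test is valid. For comparisons that stay at stool level, such as trace and invalid results, use a cluster-adjusted McNemar test or GEE with the child as cluster.

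The cost is a few sentences and a few lines of code, with no extra children or samples. Over the assumed range of correlations, clustered sample-level intervals would be about 14% to 30% wider than unadjusted ones (√1.3 = 1.14, √1.7 = 1.30).

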2. OBJECTIVES

2.1. Primary Objective

To determine the diagnostic accuracy of Xpert MTB/Rif Ultra performed on stools processed using four different sample processing methods (standard and optimized sucrose-flotation; One Step and SPK methods) in children with presumptive TB, using an intention-to-diagnose analysis.

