4.3. Sample size

As we want to estimate two proportions, specificity and sensitivity, we need to ensure a sufficient sample size for these two estimates.

The first stage is to estimate specificity by enrolling children with presumptive TB. With an expected specificity of Ultra in stool of 90%, the minimum sample size to estimate specificity with 5% precision, is 140 children with presumptive TB and negative TB culture from two respiratory samples. Inflating this number by 15% for attrition (to a total of 160 children) and considering a 10% prevalence of culture-confirmed TB in our population, we will need to enrol a total of 177 children with presumptive TB.

The second stage is to estimate sensitivity among presumptive TB children with culture confirmed TB. With an expected sensitivity of Ultra in stool of 60%, based on a literature review, the minimum sample size to estimate sensitivity with 10% precision, is 93 children with culture-confirmed TB. Inflating this number by 10% for attrition and invalid results, we will need a total of 103 confirmed TB cases. We expect 16 culture confirmed to be enrolled during the first stage (10% of 160 children enrolled in the prospective cohort). Then we will need to enrol an additional 87 children during the 2nd stage from presumptive TB children with a respiratory sample positive with Xpert Ultra (enrichment cohort). Knowing that only 90% of these children will ultimately be culture positive, we will need to further inflate the number of children to be recruited based on Ultra result in their respiratory sample [84]. We will therefore a total of enrol 97 children with Xpert Ultra positive results during the second stage.

Given routine site data and estimated enrolment figures for the Ugandan and Zambian study site, we expect to enrol children for the first stage in approximately 12 months, and Ultra-positive children for the second stage in 11 months.

For the secondary endpoints, in order to test Kappa coefficients with a minimum acceptable value of 0.4 [47], considering the study sample size, we will be able to detect a minimum change of 0.1 in Kappa coefficient between the stool sample processing methods with 80% power.

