8.2. Laboratory assessment

8.2.1. Xpert MTB/RIF Ultra

Ultra testing will be done at the trial laboratory on standard GeneXpert platforms for the two respiratory samples and the two stools samples.

The Ultra assay will be carried out according to the manufacturers' guidelines and will be defined as positive, negative or indeterminate based on the manufacturers' recommended criteria.

Results will be interpreted as follows:

- In case of positive result for the presence of MTB (including "trace call" positive result) on any
 respiratory sample or stool sample processed with the sucrose flotation method, the global result
 will be given as "MTB detected".
- In case of negativity of Ultra performed on the two respiratory samples and the two stool samples processed with the sucrose flotation method, the global result will be given as "MTB not detected".
- In case of an invalid or error result for MTB detection, the test will be repeated if sample volumes allow for it.
- In case of rifampicin resistance detected on one or more sample, the result will be given as "MTB detected, rifampicin resistance detected". Otherwise the result will be given as "MTB detected, rifampicin resistance not detected (or indeterminate)". Children with rifampicin resistance detected by Ultra will have culture and phenotypic DST performed on leftovers from stool and respiratory samples (with additional samples taken if needed), and will be started on empirical MDR-TB treatment according to national guidelines.

Xpert Ultra results will be communicated to the study nurse by message by the laboratory technician and to the treating physician as soon as available. If positive, TB treatment will be initiated immediately.

For stools, only Ultra results from stools processed with the sucrose flotation method will be communicated to the clinician as this is the only method published and validated in a clinical study. Results from Ultra assay on stools processed with the SPK, STEP method and sucrose flotation optimized method will not be disclosed.

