Statistical analysis (primary endpoint):

Sensitivity of Ultra on stool using TB culture reference standard (LJ and MGIT) in respiratory sample: point estimate and 95% CIs.

Specificity of Ultra on stool using TB culture reference standard (LJ and MGIT) in respiratory sample: point estimate and 95% CIs.

An intention-to-diagnose analysis will be performed at sample level (denominator: total number of samples collected) and patients level (denominator total number of cases with at least one stool sample collected). Invalid Ultra results and contaminated culture results will be classified as negative.

Expected results:

Evaluation of the diagnostic accuracy and feasibility of each of the four stool processing methods.

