Methods tested at 10 ² CFU/g	- Manual shaking - Sed 30' - 0.5 g - No filtration - dilution ratio 1:5	- Manual shaking - Sed 30' - 1 g - No filtration - ratio 1:5	- Manual shaking - Sed 30' - 0.5 g - Gauze filtration - ratio 1:5
Invalid Index vs reference method	10% vs 6%	11% vs 0%	10% vs 6%
Errors Index vs reference method	0% vs 0%	0% vs 0%	0% vs 0%
Sensitivity* Index vs reference method	53% vs 58%	11% vs 22%	30% vs 58%
Mean CTs IS6110- 1080** Index vs reference method	25.9 vs 27.4	27.2 vs 29.1	26.4 vs 27.4
Mean CTs SPC*** Index vs reference method	28.6 vs 29.1	29.1 vs 29.2	29.1 vs 29.1

* Sensitivity = Proportion of TB detected among all samples; invalid results and errors are counted as negative results.

** CT IS6110-1080 = Cycle thresholds of the two multicopy M. tuberculosis-specific amplification targets (IS6110 and IS1080)

*** CT SPC = Cycle thresholds of the internal Xpert Sample Processing Control

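### Counting an invalid stool Ultra as negative scores failed runs as true negatives, so primary specificity rises slightly with a method's failure rate

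*Protocol*

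**What the plan says.** Section 2.1 asks for the accuracy of the four methods "in children with presumptive TB, using an intention-to-diagnose analysis". Section 11.2.1 makes sensitivity and specificity of each method primary, with 95% confidence intervals, and sets two denominators: "Sample level (denominator: total number of samples collected): 1 stool vs the TB culture reference standard" and "Patient level (denominator total number of cases with at least one stool sample collected". It then states: "Invalid Ultra results, contaminated and NTM culture results will be considered negative". Appendix 1 repeats the rule: "Invalid Ultra results and contaminated culture results will be classified as negative". Neither place makes the handling of an invalid stool result depend on the child's culture result.

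Three other places bear on the point:

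- Section 8.2.1, on running the assay: "In case of an invalid or error result for MTB detection, the test will be repeated if sample volumes allow for it".
- Appendix 2, the footnote to the in-vitro table: "Sensitivity = Proportion of TB detected among all samples; invalid results and errors are counted as negative results". That convention is stated for sensitivity only.
- Section 11.2.2, secondary analyses: a per-protocol analysis without invalid Ultra results, and a McNemar comparison of the invalid proportions between methods.

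This point concerns only the invalid stool Ultra result, not the part of the rule about contaminated or NTM cultures.

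**The concern.** An intention-to-diagnose analysis keeps failed tests in the denominator so that a method cannot profit from them. For sensitivity the rule does this: a failed run in a culture-positive child is a miss. For specificity it works the other way, because a failed run in a culture-negative child enters the numerator as a correct result.

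Specificity is half of the primary endpoint and the reason for stage 1. Failure rates can be expected to differ between methods: Appendix 2 reports 10% invalid for the optimised sucrose method against 6% for the reference method. If the primary rule also governs the paired specificity comparison in Section 11.2.2, a stool that is false positive by one method and invalid by the other becomes a discordant pair in favour of the method that failed.

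**Working it through.** **The plan's own figure.** Section 4.3: "With an expected specificity of Ultra in stool of 90%, the minimum sample size to estimate specificity with 5% precision, is 140 children". With n = 1.96² × p(1 − p)/d², p = 0.90 and d = 0.05, n = 138.3, so 139 against 140 stated. The figure reproduces and is not in question.

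**Inputs**
- Sp, specificity on valid runs: 90% (Section 4.3). As the other end, 99%, the value Section 4.1 cites for Xpert MTB/RIF on stool (not Ultra).
- v, invalid proportion: 6% and 10% (Appendix 2, reference and optimised sucrose methods, spiked stools). The study's own rates are not known.
- n = 140 culture-negative children, one stool each.
- Assumption: failure is unrelated to whether the run would have been positive.

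**Formulas, sample level**
- Plan's rule: (1 − v)Sp + v
- Valid runs only: Sp
- Gain of the rule over valid-only: v(1 − Sp)
- Valid negatives among all culture-negative stools: (1 − v)Sp

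| Sp | v | Plan's rule | Valid only | Gain (points) | Valid negative, all stools |
|---|---|---|---|---|---|
| 90% | 6% | 90.6% | 90.0% | 0.6 | 84.6% |
| 90% | 10% | 91.0% | 90.0% | 1.0 | 81.0% |
| 99% | 6% | 99.06% | 99.0% | 0.06 | 93.06% |
| 99% | 10% | 99.1% | 99.0% | 0.1 | 89.1% |

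**In counts, at 10% and 90%.** 14 runs fail and 126 are valid. Of these, 12.6 are false positive and 113.4 are valid negatives. The plan scores (113.4 + 14)/140 = 91.0%. Counting failures against the method gives 113.4/140 = 81.0%.

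**Direction between methods.** Take two methods with the same Sp of 90% and 6% and 10% invalid. The plan's rule puts the method that fails more 91.0 − 90.6 = 0.4 point ahead. The figure over all stools puts it 84.6 − 81.0 = 3.6 points behind.

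**Patient level.** Under Section 11.2.1 a child with one invalid and one negative stool is negative on a valid result. Only a child with no valid stool is scored negative on nothing. If u is the share of such children, the gain over specificity among children with a valid result is u(1 − Sp). If the two stools fail independently, u = v², which is 0.36% at v = 6% and 1% at v = 10%, so the gain at 90% is about 0.04 to 0.1 point. If failures cluster within a child, u moves towards v and the gain towards the sample-level figure.

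**Sensitivity under the same rule.** 60% × (1 − v) = 56.4% at 6% and 54.0% at 10%.

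**Extremes only.** At v = 20% (the drop threshold in the in-vitro selection rule) the gain at 90% is 2.0 points. At v = 50% (5 of 10 results in one Table 1 study of Xpert MTB/RIF) it is 5.0 points. Neither is an expected rate for this study.

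**The case against.** The strongest reply is that treating no positive result as negative on both sides is a consistent intention-to-diagnose rule, openly stated, and that the plan already holds the means to see its effect. The per-protocol analysis gives accuracy without invalid results, and the invalid proportions are compared between methods. At the in-vitro rates the distortion between methods is 0.4 point, about half a child in 140, against a planned precision of 5 points. Repeat testing under Section 8.2.1 can lower the final invalid rate further.

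Most of this stands, and it limits the size of the point. It does not remove it. Both analyses are secondary and leave the primary specificity as it is. The per-protocol analysis also drops contaminated and NTM cultures, so it does not isolate the effect of invalid stools.

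Three stronger readings are tempting, but the documents do not support them:

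- **That a method profits overall by failing.** It does not. At 10% invalid and 90% specificity, specificity gains 1 point and sensitivity loses 6. A method that always failed would score 100% specificity and 0% sensitivity.
- **That failures are hidden.** They are not. The invalid proportion is a named secondary endpoint with its own paired test.
- **That Section 8.2.1 contradicts Section 11.2.1.** It does not. It covers repeat testing and reporting to clinicians, and does not say how a result still invalid after a repeat is analysed.

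It is also fair that making valid-only specificity the sole primary figure would depart from the intention-to-diagnose objective in Section 2.1. The fix therefore has to carry a figure over all stools or children as well.

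**Conclusion.** The point holds and is modest. As written, the primary specificity rises with the proportion of failed runs, which is the wrong direction for an intention-to-diagnose figure. Over valid-only specificity the inflation is about 0.6 to 1.0 point at 6% to 10% invalid and 90% specificity, about 0.1 point or less at 99%, and smaller at patient level or after successful repeats. The larger gaps between the plan's figure and the valid-negative proportion (91% against 81% at 10% invalid) compare two different quantities. They show what the primary figure leaves out and should not be read as the bias in specificity.

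The sizes rest on in-vitro failure rates, on failure being unrelated to the result the run would have given, and, for the patient-level figures, on independent failure of the two stools. The direction needs none of the assumed rates. A correction is worthwhile because it concerns a primary figure and costs little.

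**What to change.** In Section 11.2.1 and Appendix 1:

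1. Keep invalid as negative for sensitivity.
2. For specificity, do not score an invalid result as a true negative. In the primary table show invalid as a separate row for each method, and report together (a) specificity among stools or children with a valid result and (b) the proportion of all culture-negative stools or children with a valid negative result. Figure (b) is the intention-to-diagnose figure with failures counted against the method.
3. At patient level, class a child as invalid only if no stool gave a valid result.
4. In the McNemar comparison of specificities, use pairs valid by both methods. Compare the invalid results separately, as Section 11.2.2 already plans.

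Cost: protocol wording and one table row per method, with no new data. The specificity shown becomes less favourable or slightly less precise. At 10% invalid and 90% specificity, the half-width for (a) goes from about 5.0 points (n = 140) to 1.96 × √(0.90 × 0.10/126) = 5.2 points. For (b) it is 1.96 × √(0.81 × 0.19/140) = 6.5 points. The paired comparison also loses pairs: at 6% and 10% invalid, failing independently, 0.94 × 0.90 × 140 ≈ 118 of 140 remain.

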3. STUDY ENDPOINTS

3.1. Primary study endpoint

Sensitivity and specificity of Ultra on stool using TB culture reference standard (LJ and MGIT) in two respiratory samples (two sputums or two gastric aspirates according the age of the child). Positive: at least one positive MTB culture result in one of the two respiratory samples Negative: negative culture results from 2 samples without any positive result

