8.2.2. Mycobacterial culture

Culture will be done at the trial laboratory on two respiratory samples (ES or GA). Mycobacterial culture will be done in liquid medium (MGIT) by an automated method (BACTEC 960), and on solid media (Lowenstein Jensen) if available. Identification of mycobacteria will be done by the molecular method Gen-Probe, or Niacin test, or MPT64 antigen test depending on availability at the laboratory level. Detection of TB drug

resistance will be performed using first-line drug sensibility testing (DST) on liquid media (MGIT) or solid media or line probe assays (LPA).

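### The primary analysis counts contaminated cultures as TB-negative, against the protocol's own two-negative-culture definition, and so understates specificity slightly

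*Protocol*

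**What the plan says.** Section 3.1 defines the reference standard as culture of two respiratory samples, and a negative as "Negative: negative culture results from 2 samples without any positive result". Section 11.2.1 repeats that definition and sets the other side as "Positive: at least one positive MTB culture result in one of the two respiratory samples". Section 4.3 sizes specificity on "140 children with presumptive TB and negative TB culture from two respiratory samples".

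Section 11.2.1 then closes with: "Invalid Ultra results, contaminated and NTM culture results will be considered negative". Appendix 1 says the same, without NTM, under both the primary endpoint and the statistical analysis: "Invalid Ultra results and contaminated culture results will be classified as negative".

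Contaminated cultures are set aside only in the secondary per-protocol analysis of section 11.2.2, which works by "excluding invalid Ultra results, contaminated and NTM culture results from analysis". For contamination, that section adds that "to be excluded both culture results per sample will need to be contaminated". Section 8.2.2 plans liquid culture for every sample "and on solid media (Lowenstein Jensen) if available", so a second medium is not assured.

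**The concern.** Counting an unreadable stool Ultra as negative is sound, because the index test had its chance and did not detect TB. A contaminated culture is different: the reference standard failed and says nothing about disease. Under the closing sentence of 11.2.1, a child with both samples contaminated, or one contaminated and one negative, is TB-negative without the two negative results that the same section asks for. Two statisticians working from 11.2.1 could build different 2x2 tables, one from the definition and one from the closing sentence.

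At stake is primary specificity. A child who has TB, is stool-positive, and has no positive culture because of contamination is counted as a false positive of the stool test. The planned analyses do not separate this out. The per-protocol analysis removes contaminated cultures and invalid stool results together, so a difference from the primary result cannot be attributed to either.

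**Working it through.** **Reproducing the plan's figures (section 4.3).** With n = 1.96² p(1-p)/d²:
- Specificity 90%, precision 5 points: 138.3, so 139 (stated 140).
- Sensitivity 60%, precision 10 points: 92.2, so 93 (stated 93).
- Stage 1: 140 × 1.15 = 161 (stated 160); 160/0.9 = 177.8 (stated 177).

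The plan's numbers hold within rounding.

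**Inputs for the bias.**
- Stage 1 enrolment 177 and TB prevalence 10% (section 4.3), giving T = 17.7 TB and N0 = 159.3 non-TB children. The 10% is taken as the prevalence before any loss to contamination.
- Stool sensitivity Se = 60% (section 4.3).
- True specificity Sp = 90% (section 4.3), or 99% (cited in section 4.1 for the older Xpert assay on stool).
- f = share of TB children left with no positive culture because of contamination. The documents give no value; 2 to 20% is an assumption.
- Contamination in non-TB children is taken as unrelated to their stool result.

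**Formula.** Under the rule, T·f TB children join the culture-negative group, and a fraction Se of them are stool-positive:

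apparent Sp = [N0·Sp + T·f·(1-Se)] / (N0 + T·f)

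Example, Sp = 90%, f = 10%: (143.37 + 1.77 × 0.4) / (159.3 + 1.77) = 144.08/161.07 = 89.5%.

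| f | Apparent Sp, true 90% | Bias (points) | Apparent Sp, true 99% | Bias (points) |
|---|---|---|---|---|
| 2% | 89.9% | -0.1 | 98.9% | -0.1 |
| 5% | 89.7% | -0.3 | 98.7% | -0.3 |
| 10% | 89.5% | -0.5 | 98.4% | -0.7 |
| 20% | 88.9% | -1.1 | 97.7% | -1.3 |

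At Sp = 99% and f = 10%, spurious false positives number 17.7 × 0.10 × 0.60 = 1.1, beside 159.3 × 0.01 = 1.6 real ones.

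**Sensitivity.** Its denominator is children with at least one MTB-positive culture. A TB child with no positive culture is outside that denominator whether labelled negative or not available. Estimate, denominator and interval are the same under both rules.

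**Room for exclusions.** 160 × (1 - 0.125) = 140, so the target holds for exclusions up to 12.5% if nothing else is lost. At 10% excluded, 144 remain (half-width 4.9 points at Sp = 90%); at 20%, 128 remain (5.2 points).

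**The case against.** The strongest reply is that the effect is small and foreseen. One positive culture from either sample rescues a child, so few are mislabelled. If failures were independent, 10% of children with every culture contaminated would need a per-culture rate of about 56% with four cultures (0.10^(1/4)) or 32% with two (0.10^(1/2)). Clustering within a child would lower these rates, and a child whose only positive culture is lost also counts towards f, but the upper part of the range is generous. The bias runs against the stool test, so it is conservative. All of this stands and limits the size of the point.

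It is also fair that the protocol has other safeguards. The composite standard of section 3.3 accepts a positive respiratory Xpert as confirmation, so there a contaminated culture cannot turn an Xpert-positive child into a non-case. That analysis answers a different question and leaves the primary estimate as it is.

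Two stronger readings are tempting:
- **Sensitivity is biased or loses cases because of this rule.** It does not, as shown above. Contamination itself can cost cases and precision, but excluding the affected children does not bring them back.
- **Xpert-positive enrichment children with failed cultures flood the culture-negative group.** If the 87 expected stage 2 cases entered on the same terms, the bias would be -0.7 to -5.8 points at 90% and -0.8 to -6.9 points at 99%. Section 4.1 confines specificity to the consecutively enrolled children, and section 11.2.1's silence does not cancel that. The figure shows only why 11.2.1 should repeat the restriction.

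Counting NTM growth as MTB-negative is not the same problem: the culture gave a result.

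**Conclusion.** The inconsistency is real: the closing rule of 11.2.1 and Appendix 1 contradicts the definition of culture-negative and applies an index-test convention to the reference standard. Its supported consequence is a downward bias in primary specificity. In stage 1 it is about 0.5 to 0.7 points at an assumed 10% loss, and at most 1.1 to 1.3 points at 20%. These figures rest on an assumed range for f, stool sensitivity of 60%, and specificity taken from the prospective cohort alone. Within those limits the bias is well inside the planned 5 points and would not overturn a conclusion. At a specificity near 99%, though, it could add a visible share to a handful of false positives. It is worth correcting because the primary 2x2 table should have one definition.

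**What to change.** In section 11.2.1 and in both places in Appendix 1:
- Keep invalid stool Ultra as negative, and NTM as MTB-negative, but delete contaminated cultures from the rule.
- Class a child as culture-positive if any culture is MTB-positive.
- Class a child as culture-negative only if both samples have at least one interpretable non-MTB culture, on either medium.
- Class every other child as reference standard not available, leave that child out of the culture-based specificity table, and report the number.
- State in 11.2.1 that specificity uses the prospective cohort only.

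No new samples or visits are needed. The cost is a smaller specificity denominator. The 20 children between 140 and 160 were set aside for attrition, so contamination and attrition would share that margin; the 12.5% tolerance applies only if there is no other loss.
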